#### **10.3.9. Discharge ( $\leq$ 30 days Post-Implant)**

The discharge visit window is defined as post-index procedure through 30 days whichever comes first. The visit will occur at the time of subject's discharge from the hospital, but no later than 30 days post-procedure (whichever comes first). The following evaluations will be completed and data recorded on the appropriate eCRF:

- 12-lead ECG
- Transthoracic Echocardiography (TTE)
- Relevant medications
- Adverse events/device deficiency

If the required testing is not completed as part of the subject's hospital discharge visit, it may be performed any time during the discharge visit window through 30 days post-index procedure without a protocol deviation.

#### **10.3.10. 1 Year (365 $\pm$ 30 days) Post-Procedure Follow-up Assessment**

Subjects will be seen at 1 year ( $\pm$  30 days) post-procedure. The following evaluations will be completed and data recorded on the appropriate eCRFs:

- NYHA classification
- 12 lead ECG
- Hematology/chemistry data
- Transthoracic Echocardiography (TTE)
- Relevant medications
- Adverse events/device deficiency

**10.3.11. Annual Year 2 (730 ± 60 days) Post-Procedure Follow-up Assessment**

Subjects will be seen at 2 years (730 ± 60 days) post-procedure. The following evaluations will be completed and data collected on the appropriate eCRFs:

- NYHA classification
- 12 lead ECG
- Hematology/chemistry data
- Transthoracic Echocardiography (TTE)
- Relevant medications
- Adverse events/device deficiency

**10.3.12. Annual Year 3 (1095 ± 60 days) Post-Procedure Follow-up Assessment**

Subjects will be seen at 3 years (1095 ± 60 days) post-procedure. The following evaluations will be completed and data collected on the appropriate eCRFs:

- NYHA classification
- 12 lead ECG
- Hematology/chemistry data
- Transthoracic Echocardiography (TTE)
- Relevant medications
- Adverse events/device deficiency

**10.4. Subject Accountability****10.4.1. Missed Follow-up Visits**

Every effort should be made to ensure subjects return to the clinic for all protocol required follow-up visits. If the subject is unable to return for an in-person clinic visit, the Investigator (or designee) must document the reason the subject was unable to complete the visit and, if applicable, follow the requirements for deviation reporting as outlined in Section 10.9. The Investigator should also make every effort to contact the subject within the visit window, to collect the subject's vital status (recorded on the appropriate eCRFs) as well as information related to potential adverse events (recorded on the AE eCRF).

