**Table 5. New York Heart Association (NYHA) Classification**

Class I	Subject with cardiac disease but without resulting limitations of physical activity. Ordinary physical activity does not cause undue fatigue, palpitation, dyspnea, or anginal pain.
Class II	Subjects with cardiac disease resulting in slight limitation of physical activity. They are comfortable at rest. Ordinary physical activity results in fatigue, palpitation, dyspnea, or anginal pain.
Class III	Subjects with cardiac disease resulting in marked limitation of physical activity. They are comfortable at rest. Less than ordinary physical activity causes fatigue, palpitation, dyspnea, or anginal pain.
Class IV	Subjects with cardiac disease resulting in inability to carry on any physical activity without discomfort. Symptoms of cardiac insufficiency or of the anginal syndrome may be present even at rest. If any physical activity is undertaken, discomfort is increased.

NYHA classification will be assessed at baseline and 1 through 3 year follow-up visits with the results recorded on the appropriate eCRF.

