#### **14.3.1. Secondary Endpoints**

The clinical performance endpoints are:

- NYHA Functional Classification (at 1 year and annually thereafter through 3 years)
- Clinically acceptable hemodynamic performance as measured by the following hemodynamic measurements obtained from echocardiography at discharge or  $\leq 30$  days (whichever comes first), 1 year and annually thereafter through 3 years):
  - effective orifice area (EOA)
  - effective orifice area index (EOAI)
  - peak pressure gradient
  - mean pressure gradient
  - performance index
  - cardiac output
  - cardiac index
  - valve regurgitation

No specific hypotheses have been set for the analysis of hemodynamic performance of Mosaic and Hancock II valves containing PEEK stent material at 1 year post-implant. No sample size determination is based on these secondary endpoints.

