7.4. Handling of Missing Data and Dropouts

Unless specified otherwise in each objective, no statistical techniques will be used to impute missing data. If a subject's data are missing for any reason, that subject will not be included in that portion of the analysis. The number of subjects included in each analysis will be reported so that the potential impact of missing data can be assessed.

In the case of partial dates, the general rule is as follows:

- If only the month and year are known, the event or assessment will be analyzed as if it occurred on the 15th of that month.
- If only the year is known, the event or assessment will be analyzed as if it occurred on June 30th of that year.

These resolutions of partial dates are subject to the restrictions that pre-procedure events and assessments must occur between the enrollment date and the procedure date, and post-procedure events and assessments must occur no earlier than the procedure date. If additional information about the partial dates might be known, for example, the event occurs after 15th of the month, then data may be analyzed as if it occurred on the 16th of the month.

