7.6.2.3. Data Collection and Analysis Methods

NYHA data will be collected at baseline, 1 year and annually through 3 years on the site follow-up form. Echo data will be collected at baseline, discharge through 30 days, 1 year and annually through 3 years. All transthoracic (TTE) echoes will be analyzed by an echo core lab which will determine the values for the Hemodynamic Performance endpoints.

Data Collection Requirement	Assessment Intervals					
	Baseline	Implant	Discharge through 30 days	1 Year	Annually years 2-3	Exit
Window from implant	-45 days/-180 days for TTE	Date of Mosaic and Hancock II valves with PEEK material Implant	≤ 30 days	± 30 days	± 60 days	Date of Exit
Demographics	X					

Data Collection Requirement	Assessment Intervals					
	Baseline	Implant	Discharge through 30 days	1 Year	Annually years 2-3	Exit
Window from implant	-45 days/-180 days for TTE	Date of Mosaic and Hancock II valves with PEEK material Implant	≤ 30 days	± 30 days	± 60 days	Date of Exit
Physical Examination	X					
Pregnancy Test	X*					
Medical History	X					
NYHA Classification	X			X	X	
12-Lead ECG	X		X	X	X	
Blood Labs				X	X	
Transthoracic Echo (TTE)	X		X	X	X	
Transesophageal Echocardiogram (TEE)		X				
AE/Device Deficiency		X	X	X	X	X
Relevant Medications	X		X	X	X	
EuroScore II	X					
STS Risk Score	X					
Operative Information		X				
Protocol Deviations		X	X	X	X	X
Study Exit						X

*Pregnancy test is required for female subjects who are not exempt, see CIP section 10.3.1.

NYHA functional classification and echocardiographic (TTE) hemodynamic data will be summarized using descriptive statistics for continuous variables and frequency tables for discrete variables. NYHA functional class will be evaluated based on the percentage of subjects in each specific NYHA class at each follow-up time-point.

Hemodynamic Performance endpoints will be summarized as with continuous data. These data will be summarized by aortic and mitral position.

This objective will be analyzed for the Implanted population.

8. Validation Requirements

Validation requirements will follow SAS Programmers group guidance.

9. References

Kalbfleisch, J. D. and Prentice, R. L. (1980), *The Statistical Analysis of Failure Time Data*, New York: John Wiley & Sons.

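### NYHA class is not among the items collected when a visit is missed, so its reported distribution may be too favourable; a few extra questions at the existing contact would reduce the gap

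*Protocol*

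**What the plan says.** NYHA class is one of the secondary endpoints. Protocol 14.3.1 lists "NYHA Functional Classification (at 1 year and annually thereafter through 3 years", and Protocol 10.6 names it beside valve hemodynamics as the basis for judging clinical performance.

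Collection is tied to visits. Protocol 10.3.3 says "NYHA classification will be assessed at baseline and 1 through 3 year follow-up visits", and SAP 7.6.2.3 says "NYHA data will be collected at baseline, 1 year and annually through 3 years on the site follow-up form". Table 5 of the Protocol defines the four classes by symptoms and limits on activity. No test or measurement is involved.

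For a subject who cannot come to the clinic, Protocol 10.4.1 sets one firm duty: the site "must document the reason the subject was unable to complete the visit". It adds a softer instruction, "The Investigator should also make every effort to contact the subject within the visit window", and gives its purpose: "to collect the subject's vital status (recorded on the appropriate eCRFs) as well as information related to potential adverse events". NYHA class is not mentioned, and neither document describes a remote NYHA assessment.

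On analysis, SAP 7.6.2.3 states "NYHA functional class will be evaluated based on the percentage of subjects in each specific NYHA class at each follow-up time-point". SAP 7.4 rules out imputation unless an objective specifies it, and none is specified for NYHA. It continues: "If a subject's data are missing for any reason, that subject will not be included in that portion of the analysis". The number of subjects in each analysis is to be reported. Neither document plans a sensitivity analysis for missing NYHA or a table of missing values by reason.

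**The concern.** A site that follows the plan as written can reach a non-attending subject, record that the subject is alive and ask about adverse events, yet end the contact without the functional class. That subject then leaves the NYHA denominator for the time-point.

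This would do little harm if non-attendance had nothing to do with functional class. But NYHA class measures limitation of physical activity, and such limitation is one plausible reason for not travelling to a clinic. Where that is the reason, missingness depends on the endpoint itself, and the available-case percentages lean towards classes I and II. In a study meant to show whether the stent material change harms safety or performance, that error would be in the reassuring direction.

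NYHA also differs from the other secondary endpoints. The hemodynamic measures need an echocardiogram and cannot be recovered by telephone; NYHA class can be asked at a contact the Protocol already describes.

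**Working it through.** **Plan's own figure.** There is none for NYHA: no expected distribution, no missed-visit rate, and Protocol 14.3.1 bases no sample size on the secondary endpoints. The 89 subjects in Protocol 14.2.2 and SAP section 6 concern the primary endpoint and play no part here.

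**Step 1: does the text lead to a missing value?** NYHA is recorded at attended visits (Protocol 10.3.3, 10.3.10 to 10.3.12; SAP 7.6.2.3). The missed-visit contact lists vital status and adverse events only (Protocol 10.4.1). A subject without a value is left out and nothing is imputed (SAP 7.4). So a subject who is still in the study, misses the visit and is reached by the site has no planned NYHA value at that time-point.

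**Step 2: formula.** Among subjects still in the study and reachable at a time-point, let
- m = share who do not attend,
- p_seen = share in class III/IV among attenders,
- p_missed = share in class III/IV among non-attenders.

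Reported share = p_seen. Share among all = (1 − m) × p_seen + m × p_missed. Understatement = m × (p_missed − p_seen).

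**Step 3: illustration.** All inputs are assumptions. I take p_seen = 5% and m = 10% or 20%. Those two values match the first-year attrition allowances (10% in Protocol 14.2.2, 20% in SAP section 6), but attrition is not the missed-visit rate, so they are only stand-ins.

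| p_missed | All subjects, m = 10% | Understatement | All subjects, m = 20% | Understatement |
|---|---|---|---|---|
| 0% | 4.5% | −0.5 points | 4.0% | −1.0 points |
| 5% | 5.0% | 0 | 5.0% | 0 |
| 20% | 6.5% | 1.5 | 8.0% | 3.0 |
| 40% | 8.5% | 3.5 | 12.0% | 7.0 |
| 50% | 9.5% | 4.5 | 14.0% | 9.0 |

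For example, with m = 10% and p_missed = 20%: 0.9 × 5% + 0.1 × 20% = 6.5%, against 5.0% reported. The first row shows the sign reversing when non-attenders are better off than attenders.

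**Step 4: against sampling error.** With 90 subjects assessed (100 implanted, 10% missing) and 5% in class III/IV, the standard error is √(0.05 × 0.95 / 90) = 0.023, or 2.3 points. A shift of 1.5 to 3.5 points is about 0.7 to 1.5 standard errors.

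**Step 5: what the fix recovers.** Take m = 10%, p_seen = 5%, p_missed = 50%, so the share among all is 9.5%. If NYHA is obtained remotely from a fraction r of non-attenders, chosen without regard to class, the reported share is (0.9 × 5% + 0.1 × r × 50%) / (1 − 0.1 × (1 − r)).
- r = 0: 5.0%, gap 4.5 points
- r = 0.5: 7.0% / 0.95 = 7.4%, gap 2.1 points
- r = 0.8: 8.5% / 0.98 = 8.7%, gap 0.8 points
- r = 1: 9.5%, gap 0

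**The case against.** The strongest reply is that no bias has been shown. Protocol 10.4.1 covers absence for any reason, and visits missed through work, travel or feeling well would leave no bias or reverse it. That stands: a reader might infer that the missing values belong to subjects too ill to travel and that the table is too favourable, but the documents contain nothing that establishes either.

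A reader might also infer that the contact is obligatory. It is not: documenting the reason is required, while the contact itself is something the investigator should make every effort to achieve. Nor do the documents support a bias that grows each year. A subject who misses year 1 may attend year 2, and no trend in missed visits is given.

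The remedy also has limited reach. Under Table 6, subjects who die, withdraw, are lost to follow-up or have the valve explanted leave the study, and a missed-visit contact cannot recover their NYHA class. Only retained, reachable non-attenders count, and their number is unknown.

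Some protection exists already. Visit windows of ±30 and ±60 days allow rescheduling, the reason for absence is documented, and the number analysed is reported. Serious deterioration should partly surface as a reportable serious adverse event (Protocol 12.1.2), so it would be wrong to say that worsening is simply hidden. These safeguards show how much is missing and catch severe cases. They do not supply the class of those not seen, and a move from class II to III without a hospital stay might never become a reportable event.

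Finally, nothing forbids a site from recording NYHA at the contact, and the case report forms are under separate cover (Protocol 18.4), so they may accept a remote value. Leaving this to each site, however, sits poorly with the commitment in Protocol section 7 to standardise data collection across geographies.

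**Conclusion.** The gap in the text is real: the missed-visit contact omits a symptom-defined secondary endpoint that it could capture, and the available-case rule then removes those subjects from the NYHA percentages. Whether this distorts the result cannot be determined from the documents. The distribution may be too favourable if functional limitation is among the reasons for absence. The illustrative understatement of 1.5 to 3.5 points at 10% non-attendance rests on assumed class III/IV shares of 5% among attenders and 20% to 40% among non-attenders, and it applies only to retained, reachable subjects.

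Severity is low. NYHA is descriptive, with no hypothesis and no sample size resting on it, and the historical comparison in Protocol 14.3.1.1 concerns hemodynamic performance. A reader should not carry the point over to the primary endpoint. Vital status and adverse events are what the contact does collect, so the freedom-from-event analysis is unaffected. The change merits making because it costs little, and functional class not asked at the time may not be reliably recovered later.

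**What to change.** - **Protocol 10.4.1:** add NYHA class, asked from the Table 5 wording, to the items collected at the missed-visit contact, with an in-person/remote flag on the case report form.
- **SAP 7.6.2.3:** report the NYHA percentages at each time-point both with and without remote values, and tabulate missing NYHA by the documented reason for the missed visit.

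The cost is a few questions at a contact already described, one form flag, and one or two SAP sentences with a small table. The sample size, visit schedule and primary analysis do not change. Because Protocol 16.5 requires ethics board approval before a protocol revision is implemented, the change is best carried with the next amendment. The downside is that remote NYHA is somewhat less reliable than an in-person assessment; the flag and the two-way presentation let readers judge that. Subjects who cannot be reached stay missing and would appear in the table by reason.

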**10.4.2. Unscheduled Follow-up Visits**

If a subject returns to the institution between the protocol-required follow-up visits for a study valve-related complication, the visit will be treated as an unscheduled visit, and the assessments completed at this visit will be done at the discretion of the Investigator. The reason for the unscheduled visit as well as any assessment data will be recorded on the appropriate eCRFs and AE data on the AE eCRF.

**10.4.3. Emergency Use**

To allow for adequate time for the subject to provide informed consent, emergency cases are not allowed under this protocol.

## 10.5. Subject Consent

Geography-specific templates of the Patient Information and Informed Consent Form (PI /ICF) are provided under separate cover. These templates may be modified to suit the requirements of the individual site. For US sites, this must include Health Insurance Portability and Accountability Act (HIPAA) Authorization language. This language may be incorporated into the consent form or if required by the IRB, included as a separate document.

Medtronic, the Competent Authorities (CA), and site Ethics Board shall approve all informed consent documents prior to implementation in the study. Medtronic, Ethics Board, and CAs, where applicable, must pre-approve all language changes to the PI/ICF throughout the course of the study prior to implementation. The original Ethics Board-approved PI/ICF must be retained at the investigational site, and a copy sent to Medtronic prior treatment with study device. Any updated PI/ICF must be sent to Medtronic upon approval of the materials by the Ethics Board.

Medtronic will provide any important new information that impacts the health, safety or welfare of study subjects, for inclusion in PI/ICF updates as it becomes available. Sites should follow any Medtronic, CA or Ethics Board requirements for disseminating new information and re-consenting subjects during the course of the study.

The Investigator or authorized designee must administer the approved PI/ICF to each prospective study subject without coercion or undue improper influence on, or inducement of, the subject to participate. During the consent discussion the Investigator (or designee) must fully inform the subject of all aspects of the study relevant to the subject's decision to participate, using native non-technical language that is understandable to the subject. The subject must be informed about their right to withdraw from the study at any time and for any reason without sanction, penalty, or loss of benefits to which the subject is otherwise entitled, and also informed that withdrawal from the study will not jeopardize their future medical care. The subject must also be informed that participation in the study does not waive or appear to waive the subject's legal rights. The subject must have ample time and opportunity to read, inquire about details of the study and understand the informed consent form; and to decide whether or not to participate in the clinical study. All questions about the study should be answered to the satisfaction of the subject. All items discussed in the PI/ICF must be explained.

Informed consent will be obtained in writing from the subject. The date of consent and process by which the consent was obtained (including documentation of special circumstances, if applicable; see Section 10.5.1) will be documented in the subject's medical record prior to any study-specific procedures. Subject informed consent must be obtained in accordance with the national and local laws, regulations and guidelines of each site. The institutional standard procedure consent form does not replace the study PI/ICF.

The subject's signature and date of consent serve to document that they understand the written and verbal information that the Investigator (or designee) provides, and their agreement to participate. The Investigator or authorized delegate who conducted the informed consent process must provide their handwritten signature and date the consent was completed on the PI/ICF. The PI or qualified designee will document the informed consent process, including the date of consent and name of person conducting the consent process in the subject's medical record. The original signed consent form will be retained in the subject's study records. A copy of the signed informed consent will be provided to the subject and a copy of the signed consent will be placed in the subject's medical record.

### **10.5.1. Special Circumstances for Informed Consent Process and Signature**

If a subject cannot read or write, an impartial witness must be present during the entire informed consent discussion. The written informed consent form and any other information shall be read aloud and explained to the subject and witness. The witness signs and personally dates the informed consent form attesting that the information was accurately explained and that informed consent was freely given. The subject will sign and date if possible. Notation should also be in the subjects' medical record that a witness signed the consent attesting that the information was accurately explained and that informed consent was freely given in the case where the subject is unable to sign consent.

### **10.6. Assessment of Clinical Performance**

An Interim report on the study will be conducted at the completion of all subject's 1 year follow-up visit. Secondary endpoints used to evaluate the clinical performance will be conducted through a review of valve hemodynamics and NYHA functional classification.

### **10.7. Assessment of Safety**

An Interim report on the study will be conducted at the completion of all subject's 1 year follow-up visit. The primary endpoint will be used to measure the safety of the study device. Primary endpoint adverse events of valve related death, and reintervention of, or explant related to the Mosaic and Hancock II valves with PEEK stent material will be regularly reviewed by an independent CEC. All device and therapy related adverse events will be collected throughout the study.

### **10.8. Recording Data**

eCRFs are recommended to be entered into the RDC system within 10 days of the completion of the all follow-up visits, or sooner as requested by the sponsor.

Data entered must be traceable to source documents. Source documentation is defined as the first time data appear, and may include original documents, data and records (e.g., hospital records, clinical and office charts, procedure reports, laboratory notes, memoranda, subjects' diaries or evaluation checklists, pharmacy dispensing records, recorded data from automated instruments, copies or transcriptions certified after verification as being accurate copies, microfiches, photographic negatives, microfilm or magnetic media, x-rays, subject files, and records kept at the pharmacy, at the laboratories and at medico-technical departments involved in the clinical study).

The eCRFs (or paper copies) may not serve as source documents. Source documentation for data elements not routinely captured in medical records (e.g. echocardiography variables) may vary from site to site; the site may use source document worksheets if identified as source documents.

